During the factor or BPA prophylaxis period, patients will continue FVIII, FIX, or BPA prophylaxis as treatment for hemophilia on a regimen consistent with recommendations in the approved prescribing information, allowing for adjustment to individual patient response, and designed to decrease spontaneous bleeding. Dose and mode of administration will be per Investigator discretion; bleeding episode management should be per the local standard practice for episodic use of factors or BPAs and as per Investigator discretion. The subgroup of Cohort A patients who are not responding adequately to BPA prophylaxis treatment will not participate into this BPA prophylaxis period and will directly start the fitusiran treatment period after the screening period. All patients will continue to receive FVIII, FIX, or BPA prophylaxis for the first 7 days of the onset period. Subsequently, breakthrough bleeding episodes will be treated with on-demand factor or BPA therapy as necessary per the bleeding episode management guidelines. For the United States specific requirements, see [Section 11.6.1.1](#).

Duration of treatment

The duration of treatment with fitusiran is 7 months. The estimated total time on study, inclusive of Screening, for each patient is up to 15 months for patients who enroll in the extension study except for patients in the subgroup of Cohort A, which is up to 9 months. The estimated total time on study may be up to 21 months (up to 15 months in patients in the subgroup of Cohort A) in patients who do not enroll in the extension study due to the requirement for an additional 6 months of follow-up for monitoring of AT levels.

Statistical methods

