b Fitusiran as prophylaxis treatment and permitted on-demand use of factors or BPAs for treatment of breakthrough bleeding episodes. Patients may continue their routine factor or BPA administration schedule for up to the first 7 days of the onset period. For the United States specific requirements see [Section 11.6.1.1](#).

c Not required at Early Termination Visit for patients who complete assessment at EOT Visit and subsequently Early Terminate.

- d* Patients who discontinue study drug dosing for any reason and agree to complete the remaining assessments through the EOS/ET and AT FU visits and may receive treatment consistent with local standard practice for their disease per Investigator judgement, as applicable. For patients who withdraw from the study early and do not consent to complete remaining assessments through the EOS/ET and AT FU visits, every effort should be made to conduct the assessments performed at the EOS/ET visit.
- e* Patients not enrolling in the extension study will complete AT F/U visits at monthly intervals following final fitusiran dose until AT activity level returns to ~60% (per the central laboratory), or per Investigator discretion in consultation with the study Medical Monitor.
- f* The complete medical history/disease history (ie, including bleeding episode and treatment history over the prior 6 months) to be recorded at Screening.
- g* eDiary training will be completed at the Clinic at Screening (see [Section 7.2.1](#)).
- h* A full physical examination will be performed at Screening only; a directed physical exam will be performed at all other visits (see [Section 7.6.3](#)).
- i* Height will be recorded only at Screening for patients > 18 years old. Height for patients < 18 years old and weight for all patients will be recorded at all checked visits ([Section 7.6.2](#)).
- j* 12-lead ECGs will be performed in triplicate. On Day 1, 12-lead ECGs will be performed predose and 4 hours (± 30 min) postdose (see [Section 7.6.4](#)). The Month 7 12-lead ECG will be performed only in those patients who are performing the ET visit and may be performed in singlicate.
- k* Hepatitis C virus antibody positive patients only. FibroScan where available, otherwise FibroTest and APRI.

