4 INVESTIGATIONAL PLAN

4.1 SUMMARY OF STUDY DESIGN

The ATLAS-PPX trial (ALN-AT3SC-009) is a multicenter, multinational, open-label, Phase 3 study designed to characterize the efficacy and safety of fitusiran in male patients, aged ≥ 12 years, with severe hemophilia A or B, previously receiving factor or BPA prophylaxis. The study consists of 2 cohorts: Cohort A will consist of patients with inhibitory antibodies to Factor VIII or Factor IX; Cohort B will consist of patients without inhibitor antibodies to Factor VIII or Factor IX. A subgroup of Cohort A patients will include hemophilia B patients with inhibitory antibodies to Factor IX who are not responding adequately to BPA prophylaxis treatment (historical ABR ≥ 20) (see Inclusion Criteria in [Section 5.1](#)). The study has 3 periods defined by type of prophylaxis regimen (for the United States specific requirements, see [Section 11.6.1.2](#)):

- 6-Month factor or BPA prophylaxis period in which patients will continue their prestudy, regularly scheduled prophylaxis regimen with factors or BPAs

The subgroup of Cohort A patients who are not responding adequately to BPA prophylaxis treatment will not participate in this 6-Month BPA prophylaxis period and will start to directly receive fitusiran (in the 1-month onset period described below) after the screening period.

- 1-Month onset period in which patients receive first dose of fitusiran while continuing their factor or BPA prophylaxis for up to 7 days
- 6-Month fitusiran efficacy period in which patients receive fitusiran as prophylaxis.

Together, the 1-month onset period and the 6-month fitusiran efficacy period constitute the fitusiran treatment period.

Bleeding events and doses of factor concentrates or BPAs administered during the conduct of the study will be recorded in an electronic Diary (eDiary), as described in [Section 7.2.1](#). Since bleeding episodes are recorded as an efficacy assessment of fitusiran, these will not be treated as AEs unless they meet any of the SAE criteria listed in [Section 7.6.6.1](#). Safety, quality of life, pharmacodynamic, and pharmacokinetic data will also be collected.

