On-demand use of factor concentrates or BPAs is defined as the use of these agents, as needed, for episodic bleeding, and not on a regular regimen intended to prevent spontaneous bleeding. Throughout the study, patients in the fitusiran treatment period may receive on-demand treatment for breakthrough bleeding episodes with factors or BPAs, as appropriate. For patients in the fitusiran treatment period who have received at least 1 dose of fitusiran and are being treated for breakthrough bleeding episodes, it is recommended to follow the guidelines provided in [Section 6.3.2](#) per Investigator discretion.

Following the screening and prophylaxis periods or following the screening period for the subgroup of Cohort A enrolling directly into the fitusiran treatment period all patients will be treated with fitusiran for a total of 7 months. Therefore, the overall fitusiran treatment period is

defined as the onset period (Day 1-28 after receipt of the first dose, during which the AT lowering capacity of fitusiran is increasing but has not yet reached therapeutic levels) plus the efficacy period (Day 29 and after, when the AT lowering capacity of fitusiran has achieved therapeutic target range). For the United States specific requirements, see [Section 11.6.1.2](#).

[figure not shown]
Any current surgery occurring close to the date of the Screening visit must have surgery-related hemostatic treatment completed at least 72 hours prior to Screening. Patients may undergo unplanned or emergency surgery during the study but must not schedule non-urgent surgery to occur during the study. Perioperative guidance should be followed as specified in [Section 6.6](#).

A study Steering Committee, composed of experts in the field of hemophilia, will advise the Sponsor on study design and conduct ([Section 4.6](#)).

An independent data monitoring committee (DMC) will oversee the safety and overall conduct of this study as described in [Section 4.7](#).

The study design schema is presented in [Figure 1](#). Patients who complete the study may be eligible for an open-label extension study.

Figure 1 - Study design

[figure not shown]
Abbreviations: AT=antithrombin

Note: For subgroup of Cohort A patients enrolling directly into the fitusiran treatment period, see [Figure 2](#).

Note: For the United States specific requirements, see [Section 11.6.1.2](#).

^a Patients will continue to receive prescribed factor or BPA prophylaxis for the first 7 days of the onset period.

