6.3.1 Factor concentrates or bypassing agent prophylaxis

6.3.1.1 Routine use of factor or bypassing agent prophylaxis in the factor or bypassing agent prophylaxis period

During the factor or BPA prophylaxis period, patients will continue to receive prophylaxis with their usual products on a regimen consistent with recommendations in the approved prescribing information, allowing for adjustment to individual patient response, and designed to decrease spontaneous bleeding. The regimen used during the factor or BPA prophylaxis period must have a minimum frequency of administration as presented in [Table 5](#). The subgroup of Cohort A patients who are not responding adequately to BPA prophylaxis treatment will not participate in this BPA prophylaxis period and will directly start the fitusiran treatment period after the screening period. For the United States specific requirements, see [Section 11.6.1.2](#).

Table 5 - Factor or bypassing agent prophylaxis requirements

| Type of Factor or BPA replacement | Frequency of administration |
|-----------------------------------|-----------------------------|
| Standard half-life FVIII | Twice weekly |
| Extended half-life FVIII | Once weekly |
| Standard half-life FIX | Once weekly |
| Extended half-life FIX | Once biweekly |
| aPCC | Twice weekly |
| rFVIIa | Every other day |

Abbreviation: aPCC= activated prothrombin complex concentrates; BPA=bypassing agent; FVIII = Factor VIII; FIX = Factor IX; rFVIIa=recombinant Factor VIIa Note: For the United States specific requirements, see [Section 11.6.1.2](#).

6.3.1.2 Management of factor or bypassing agent prophylaxis during the transition to the fitusiran treatment period

The first 28 days of fitusiran treatment is referred to as the onset period. During the onset period AT lowering will be progressing toward therapeutic levels. Patients will continue factor or BPA prophylaxis with minimum frequency as in [Table 5](#), for the first 7 days of the fitusiran onset period. Subsequent to Day 7 of the fitusiran treatment period, factor concentrates or BPAs should be administered only for bleeding episodes or if needed in advance of invasive medical procedures. For the United States specific requirements, see [Section 11.6.1.2](#).

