6.3.2.2 Bleeding episode management recommendations for patients during the fitusiran treatment period (for the United States specific requirements, see Appendix 11.5.1.2)

Given the mechanism of action and pharmacodynamics profile of fitusiran, the factor or BPA dose necessary to safely and effectively treat breakthrough bleeding episodes in patients receiving fitusiran during the fitusiran treatment period will be lower than standardly prescribed. This is supported by data from the Phase 1 study in which bleed events were managed with factor or BPA, as well as additional modeling and ex vivo spiking data. More detailed information on the clinical experience in bleeding episode management in Phase 1 and Phase 1/2 fitusiran studies, as well as supportive nonclinical studies is provided in the Investigator's Brochure.

After administration of fitusiran, AT lowering will be progressing toward therapeutic levels. As quickly as 7 days after the initial fitusiran dose, the majority of patients will have AT levels at or below 60% residual activity. By 14 days after dosing, it is expected that 94% of patients will have AT lowering of >50%, with a median value of 66.8%. Based on these AT kinetics, it is recommended that patients continue with their standard factor or BPA regimens for the first 7 days following initiation of fitusiran dosing, with institution of the protocol-specific bleed management guidelines with reduced factor or BPA at Day 8 and beyond ([Table 6](#)).

Patients on fitusiran will be provided a written bleed management plan with appropriate dosing of factor or BPA for use during Day 1 through 7, as well as a bleed management plan with dosing for Day 8 and beyond. Thereafter the bleed management plan will be reviewed and updated at monthly visits, and new written plans provided to the patient if dosing changes.

Importantly, after Day 7 of the fitusiran treatment period, patients should not use factor, BPA, or other hemostatic agents as prophylaxis for bleeding episode prevention, including doses related to anticipated hemostatic challenges such as physical activity. For prophylaxis of bleeding episodes in patients who require operative procedures see [Section 6.6](#).

Bleed Management Guidelines Day 1 to Day 7 of Fitusiran Treatment Period:

Patients should be instructed to call the site prior to administering factor or BPA for the management of bleeding episodes. Patients should continue with their standard factor or BPA regimens.

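### The protocol makes routine factor/BPA prophylaxis on Days 1–7 of fitusiran optional in one place and required in others, so overlap can differ by up to a week within the onset ABR window

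*Protocol*

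**What the plan says.** The protocol states the rule for the first week of fitusiran at different strengths, all in current text.

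- **Optional.** Table 1 footnote b: "Patients may continue their routine factor or BPA administration schedule for up to the first 7 days of the onset period".
- **Ceiling only.** The study-design summary in Section 4.1 has patients "receive first dose of fitusiran while continuing their factor or BPA prophylaxis for up to 7 days". The synopsis study design and SAP Section 1.1 say much the same.
- **Required.** The synopsis, under reference therapy: "All patients will continue to receive FVIII, FIX, or BPA prophylaxis for the first 7 days of the onset period". Figure 1 footnote a: "Patients will continue to receive prescribed factor or BPA prophylaxis for the first 7 days of the onset period" (SAP Section 1.4 carries nearly the same note). Section 6.3.1.2: "Patients will continue factor or BPA prophylaxis with minimum frequency as in" Table 5, for the first 7 days.
- **Recommended.** Section 6.3.2.2: "it is recommended that patients continue with their standard factor or BPA regimens for the first 7 days following initiation of fitusiran dosing". Its Day 1 to Day 7 guideline then says that patients should continue.

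The US appendix repeats the split. Footnote b in Section 11.6.1.1 is permissive, while the reference-therapy text there, and the copies of Figure 1 and Section 6.3.1.2 in Section 11.6.1.2, are mandatory.

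In the SAP, onset ABR counts all bleeds in Days 1–28 (Sections 2.1.3.1 and 2.4.4.2.5). Factor/BPA consumption counts prophylaxis doses in the fitusiran treatment period (Section 2.4.4.2.7). The intercurrent-event exclusions in Section 2.1.3.1 neither remove nor adjust for Days 1–7. Section 2.3 lists continued factor/BPA prophylaxis during fitusiran, with study drug not stopped, as a deviation that removes a patient from the per-protocol set. It makes no exception for Days 1–7.

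**The concern.** A patient who stops routine prophylaxis on Day 1 complies with footnote b and breaches the synopsis, Figure 1 footnote a and Section 6.3.1.2. Antithrombin is still falling in that week: Section 6.3.2.2 puts most patients at or below 60% residual activity as early as Day 7. The same section switches to reduced bleed dosing on Day 8.

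What is at stake is the meaning of the early-period summaries. If overlap varies by which page a site read, onset ABR and consumption on fitusiran describe a mixture of exposures that nobody chose. The treatment-period ABR and the US primary ABR are touched to a smaller degree. The per-protocol wording adds a second inconsistency, because obeying the mandatory passages can itself count as a deviation.

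**Working it through.** **1. Compliance check.** Take two patients, one who stops routine prophylaxis on Day 1 and one who continues through Day 7.

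| Place | Stops on Day 1 | Continues through Day 7 |
|---|---|---|
| Table 1 footnote b and its US copy | complies | complies |
| Synopsis study design, Section 4.1, SAP 1.1 | unclear (ceiling, no stated minimum) | complies |
| Synopsis reference therapy, Figure 1 footnote a, Section 6.3.1.2, SAP 1.4 | breaches | complies |
| Section 6.3.2.2 | departs from advice | complies |
| SAP 2.3 per-protocol deviation | not flagged | flagged, read literally |

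Neither patient is clean against every row.

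**2. Share of each window.** Windows are from SAP Section 2.1.3.1 and Protocol Section 8.2.5.1 with its US copy.

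- Onset ABR, Days 1–28: 7/28 = 25%.
- Treatment-period ABR (global secondary) and US primary ABR, Days 1–190: 7/190 = 3.7%.
- Global primary ABR, Days 29–190: 190 − 29 + 1 = 162 days, of which 0 overlap. The exception is a patient with no bleeding data after Day 28, whose data count from Day 1.

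**3. Possible effect on ABR (illustration only).** Let B be the ABR on prophylaxis, and let k be the Day 1–7 bleeding rate without overlap divided by the rate with it. The documents do not give k, so I assume 1 to 3. I also set the rate from Day 8 onward equal to B. If no patient overlaps rather than all patients:

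- change in onset ABR = (7/28) × B × (k − 1)
- change in Day 1–190 ABR = (7/190) × B × (k − 1)

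The relative change in onset ABR is 0.25 × (k − 1): 0% at k = 1, 12.5% at 1.5, 25% at 2 and 50% at 3. At k = 2, with B from Protocol Tables 9 and 10:

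| B | Onset ABR without overlap | Change in Day 1–190 ABR |
|---|---|---|
| 4 (Cohort B) | 5 | 0.15 |
| 6 (Cohort B) | 7.5 | 0.22 |
| 12 (Cohort A) | 15 | 0.44 |
| 16 (Cohort A) | 20 | 0.59 |

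A mixture of sites would give only a fraction of these differences.

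**4. Bleeds available in Days 1–7.** Expected bleeds per patient = B × 7/365.25, from 0.08 (B = 4) to 0.31 (B = 16). At the planned cohort sizes:

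- Cohort A (30 patients): 30 × 12 × 7/365.25 = 6.9 to 30 × 16 × 7/365.25 = 9.2.
- Cohort B (50 patients): 50 × 4 × 7/365.25 = 3.8 to 50 × 6 × 7/365.25 = 5.7.

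One bleed annualizes to 365.25/28 = 13.0 over the onset period and 365.25/7 = 52.2 over a single week.

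**The case against.** The strongest reply is that the conflict is narrow. The synopsis study design and Section 4.1 describe patients who are continuing prophylaxis, with an upper limit on duration; they do not license stopping on Day 1. Section 6.3.2.2 ends by saying that patients should continue, and Section 6.3.1.2, the section written for this transition, is explicit. That stands: the only clearly permissive text is footnote b and its US copy. But footnote b sets no minimum, it sits in the schedule of assessments, and nothing ranks it below Section 6.3.1.2.

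The SAP also reports some of this already. Section 2.4.2 tabulates factor/BPA prophylaxis by observation period, and Section 2.4.4.2.7 summarizes prophylactic consumption on fitusiran. Neither does so by day.

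A wording amendment would reach few patients. The Amendment 05 history records 79 already enrolled, and SAP Section 2.4 counts only 2 participants on the 50 mg Q2M regimen. This stands too, and it moves most of the remaining value to the SAP.

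A reader might infer two stronger points that the documents do not support:

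- **That onset ABR has been shifted, or the global primary result compromised.** The size and direction of any shift depend on k and on how sites behaved, neither of which is given. The global primary window excludes Days 1–7 apart from the exception above. Onset and treatment-period ABR carry no formal test.
- **That the roughly 18 hemophilia B patients could go through the week uncovered, because Table 5 lists "Extended half-life FIX | Once biweekly".** About 7 of them are Cohort A patients, whose eligibility requires BPA prophylaxis. That leaves about 11, with the extended half-life share unstated. A patient with no injection due in Days 1–7 may still be within the interval of an earlier dose, and so is following the regimen. No passages conflict on this.

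**Conclusion.** The inconsistency is real and unresolved in current text: optional in Table 1 footnote b, required in the synopsis, Figure 1 footnote a and Section 6.3.1.2, and advised in Section 6.3.2.2. It allows up to 7 days' difference in overlap, over 25% of the onset ABR window and 3.7% of the treatment-period and US primary windows, and it feeds the consumption endpoint directly. The per-protocol deviation in SAP Section 2.3 conflicts, read literally, with the mandatory passages.

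Only the day shares and the textual conflict are established. The ABR figures above rest on an assumed k and an assumed rate from Day 8, and include no change at k = 1. The share of sites on each reading is unknown. This is a modest point about secondary summaries and, slightly, the US primary endpoint. It does not challenge the global primary analysis.

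**What to change.** 1. **Protocol.** Reconcile the synopsis, Table 1 footnote b, Section 4.1 with Figure 1, Sections 6.3.1.2 and 6.3.2.2, and the US copies to one rule chosen by the sponsor. This review takes no view on which rule is clinically right.
2. **SAP Section 2.3.** State whether routine prophylaxis in Days 1–7 counts as the continued-prophylaxis deviation for the per-protocol set.
3. **SAP reporting.** Using the eDiary reason-for-dosing field (Protocol Section 7.2.1), report how many patients used routine prophylaxis in Days 1–7. Show onset bleeds descriptively for Days 1–7 and Days 8–28. Fixed days are preferable to a cut at each patient's last routine dose: that date arises after baseline and reflects behavior, and a patient with no dose in the week would have no earlier interval.

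The cost is a wording amendment, one clarifying sentence and one descriptive table from data already collected. With roughly 4 to 9 bleeds expected per cohort in Days 1–7, counts and person-days will be more informative than annualized rates for that week.

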| Study visit (Month) | Screening | Factor or BPA prophylaxis period ^a | | | | | | Fitusiran treatment period ^b | | | | | | | | | | AT F/U ^{d,e} | |
|---------------------------------------|--------------|--|-------------|-------------|------------|------------|------------|---|-----------|-----------------|-----------|-----------|-----------|------------|------------|-----------------------|----------------|-----------------------|--|
| | | Month -6 | Month -5 | Month -4 | Month -3 | Month -2 | Month -1 | Onset period ^b | | Efficacy period | | | | | | | | | |
| | | | | | | | | Baseline | Month 1 | Month 2 | Month 3 | Month 4 | Month 5 | EOT | | EOS/ET ^{c,d} | | | |
| Study day (±Visit Window) | -228 to -169 | Day -168 | Day -140 ±7 | Day -112 ±7 | Day -84 ±7 | Day -56 ±7 | Day -28 ±7 | Day 1 | Day 15 ±3 | Day 29 ±7 | Day 43 ±3 | Day 57 ±7 | Day 85 ±7 | Day 113 ±7 | Day 141 ±7 | Day 169 ±7 | Day 197 ±7 | Day 225 ±7 | |
| Haemo-QOL/Haem-A-QOL ^g | | X | | | | | | X ^w | | | | | | | | | X ^q | | |
| HAL/pedHAL ^g | | X | | | | | | X ^w | | | | | | | | | X ^q | | |
| TSQM-9 ^g | | X | | | | | | X ^w | | | | | | | | | X ^q | | |
| EQ-5D ^g | | X | | | | | | X ^w | | | | | | | | | X ^q | | |
| Fitusiran Administration (Q2M) | | | | | | | | X | | | | X | | X | | X | | | |
| Perioperative Assessment ^f | | | | | | | | Continuous | | | | | | | | | | | |
| Patient Education Module Training | | X | | | | | | X | | | | | | | | | | | |
| Bleed Management Review ^s | | Review with patient at each visit and contact every 2 weeks (±4 days) between visits | | | | | | | | | | | | | | | | | |
| Bleeding Episodes/eDiary ^t | | Review with patient at each visit and contact every 2 weeks (±4 days) between visits | | | | | | | | | | | | | | | | | |
| Adverse Events ^u | | Continuous | | | | | | | | | | | | | | | | | |
| Concomitant Medications ^v | | Continuous | | | | | | | | | | | | | | | | | |

Table 1 - Schedule of assessments

| Study visit (Month) | Screening | Factor or BPA prophylaxis period ^a | | | | | | Fitusiran treatment period ^b | | | | | | | | | | AT F/U ^{d,e} |
|---------------------|---------------------------------------|---|-------------|-------------|------------|------------|------------|---|-----------|-----------------|-----------|-----------|-----------|------------|------------|------------|-----------------------|-----------------------|

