- l* Sample may be used for study of biomarkers related to hemophilia and associated conditions, investigations of emerging safety issues, or the development of fitusiran. After specified analyses are run, residual samples may be stored for up to 15 years from last patient, last visit, or as per local regulations, and used for further study of biomarkers related to hemophilia and associated conditions, investigation of emerging safety issues, or the development of fitusiran. Samples drawn from central lines may be excluded from TG analysis.
- m* To be performed in all patients, at any clinic visit during their factor or BPA prophylaxis period, with blood drawn before, 10 min (± 5 min) after, and 60 min (± 5 min) after administration of their usual prophylactic dose of factor or BPA. Laboratory testing pre- and post- factor/BPA include: Coagulation, and TG. The timing of this visit should coincide with the patient's usual prophylaxis regimen, so that pre-dose thrombin generation is at nadir and the benefit of administered factor or BPA is maintained. For the United States specific requirements see [Section 11.6.1.1](#).
- n* On fitusiran dosing days, samples will be collected within 4 hour priors to dosing. For the AT assessments, upon the first AT level <15%, the patients must have another AT activity level sample drawn within 1 week of site receipt of the results.
- o* Liver function tests (LFTs) and hepatic tests are as listed in [Table 7](#). LFTs may be obtained up to 7 days before the clinic visit on which fitusiran dosing is scheduled. LFTs performed within 7 days of Day 1 will only be used to inform dosing on Day 1 and do not need to be used to confirm eligibility. LFTs can be analyzed locally, but if a local assessment is drawn, a serum chemistry sample must also be drawn for analysis at the central laboratory. Under conditions of elevated ALT and/or AST, see [Section 6.2.3.1](#) and [Table 8](#). LFT results will be obtained prior to receiving monthly fitusiran dosing.
- p* Blood samples for PK analysis will be collected at the time points listed in [Table 11](#) in East Asian patients at East Asian sites.
- q* Must be completed at clinic. Will be collected at EOS visit; not collected at ET visit.
- r* Perioperative assessment of safety and hemostatic efficacy only in patients undergoing major operative procedures while on study drug (see [Table 12](#)).

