2.1.3.2.1 HRQOL Instruments: Haem-A-QOL and Haemo-QOL

The Haemophilia Quality of Life Questionnaire for Adults (Haem-A-QOL) and Haemophilia Quality of Life Questionnaire for Children and Adolescents (Haemo-QOL) are psychometrically tested QOL assessment instruments for patients with hemophilia. The Haem-A-QOL are provided to patients ≥ 17 years of age, and includes 46 items contributing to 10 QOL domains (physical health, feelings, view of yourself, sports and leisure, work and school, dealing with hemophilia, treatment, future, family planning, partnership and sexuality). Scoring for each item is based on a 5-point Likert scale (never, rarely, sometimes, often, and all the time), and higher scores represent greater impairment.

The Haemo-QOL (Children's short version for age groups II/III [8-16 years of age]) are provided to patients < 17 years of age.

Both Haem-A-QOL and Haemo-QOL test are assessed at Month -6, Day 1 and Month 7 visit.

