2.4.4 Analyses of efficacy endpoints

Analyses for all the primary and secondary efficacy endpoints are conducted using EAS 1 as defined in Section 2.3. Listings of ABR will be provided for participants in EAS 2.

Baseline for fitusiran treatment period is defined as the last non-missing value on or before the date of first dose of fitusiran. Baseline for factor/BPA prophylaxis period is defined as the last non-missing value on or before the enrollment date (Month -6 visit date).

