Change from baseline in Haem-A-QOL physical health score and total score (in patients ≥ 17 years of age) in the factor or BPA prophylaxis period and fitusiran treatment period are analyzed using a mixed model for repeated measure analysis (MMRM) with robust sandwich covariance matrix, with fixed effects of study period (factor or BPA prophylaxis period and fitusiran treatment period), baseline Haem-A-QoL physical health score and total score for each study period as covariates. Least square means of the physical health score and total score in each treatment period and the difference of the least square means of the physical health score and total score in the two periods (along with the 95% CI and p-value) are presented. The normality assumption based on MMRM model is examined and a sensitivity analysis based on the non-parametric Wilcoxon signed-rank test is performed. For patient with missing assessment due to early withdrawal, a sensitivity analysis is performed by imputing the domain score and total score as the worst score if the reason of withdrawal is treatment-related in the fitusiran treatment period, and as the average score for other reasons of withdrawal that are not treatment related in the fitusiran treatment period. The same analysis as main will be performed as a sensitivity analysis by excluding values of those who completed Haem-A-QoL at baseline after first dose of fitusiran.

To evaluate the impact of Covid-19, the same MMRM model will also be repeated on Covid-19 unaffected set. In addition, a sensitivity analysis using same MMRM model will be performed excluding the data impacted by Covid-19 major/critical protocol deviation. A supportive analysis will be repeated on the patients whose responses level to EQ-5D dimensions “anxiety/depression” is no change or improved from baseline of factor or BPA prophylaxis period.

Change from baseline in Haem-A-QoL physical health score and total score in the factor or BPA prophylaxis period and fitusiran treatment period are also summarized descriptively by study period.

Domain scores, standardized scale scores, and transformed scale scores for Haem-A-QoL and their changes from baseline in the factor or BPA prophylaxis period and fitusiran treatment period are summarized by study period.

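### Self-completed questionnaires are barred at the early termination visit, so patients who withdraw from the study before Month 7 have no fitusiran-period quality-of-life score; collecting them there is a cheap improvement

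*Protocol*

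**What the plan says.** **Protocol.** Table 1 attaches footnote q to the Day 197 EOS/ET cell for Haem-A-QOL/Haemo-QOL, HAL/pedHAL, TSQM-9 and EQ-5D, and also for HJHS and patient resource use. The footnote requires completion in the clinic and continues: "Will be collected at EOS visit; not collected at ET visit". It gives no reason. Footnote d says that for patients who leave early and do not consent to the remaining assessments, "every effort should be made to conduct the assessments performed at the EOS/ET visit". Section 5.3.2 asks for the same and sets a target of four weeks from the last dose. Section 5.3.1 encourages patients who only stop study drug to stay to the end of the study.

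**SAP.** Section 2.1.3.2.1 gives the timing: "Both Haem-A-QOL and Haemo-QOL test are assessed at Month -6, Day 1 and Month 7 visit". Changes in Haem-A-QOL physical health and total score (2.4.4.2.4) "are analyzed using a mixed model for repeated measure analysis (MMRM) with robust sandwich covariance matrix", with no imputation stated. For missing assessments due to early withdrawal there is one sensitivity analysis, "imputing the domain score and total score as the worst score if the reason of withdrawal is treatment-related in the fitusiran treatment period", and as an average score for other reasons. Sections 2.4.7.1 to 2.4.7.3 summarise TSQM-9, HAL/pedHAL and EQ-5D-5L descriptively, with no imputation for withdrawal.

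**The concern.** Change in Haem-A-QOL is a named secondary endpoint. Its fitusiran-period value rests on one measurement, and the schedule withholds that measurement from the patients whose absence is most likely to be informative: those who leave the study because of intolerance, bleeding or dissatisfaction. The same holds for TSQM-9, where a patient who leaves out of dissatisfaction is never asked about satisfaction on fitusiran. The score could be taken at a visit that sites are already asked to hold.

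At stake is a fitusiran-period estimate that may be too favourable and a within-patient comparison in which some patients supply only the prophylaxis-period half. The fallback analysis assigns a score where a real one might have been recorded.

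**Working it through.** Neither document gives a figure to reproduce. The check is a reading of the schedule against the analysis, followed by illustrative arithmetic.

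**1. Which scores exist.** For the fitusiran period, "Baseline for fitusiran treatment period is defined as the last non-missing value on or before the date of first dose of fitusiran" (SAP 2.4.4). The Day 1 questionnaire is therefore baseline, not outcome.

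| Patient | Prophylaxis change (Month -6 to Day 1) | Fitusiran change (Day 1 to Month 7) |
|---|---|---|
| Completes the study | yes | yes |
| Stops fitusiran, stays to EOS | yes | yes, possibly off drug |
| Withdraws from the study before Month 7 | yes | none |

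**2. What the analyses do with the third row.** In the main mixed model a withdrawer contributes at most the prophylaxis-period change. The Wilcoxon signed-rank check is paired and drops the patient. The worst/average imputation applies only to Haem-A-QOL and only as a sensitivity analysis. The SAP does not say whose average is meant or over which period.

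**3. Would a termination-visit score count as on treatment?** Protocol 5.3.2 targets four weeks, that is 28 days, after the last dose. The SAP 2.1.3.1 on-treatment rule for bleeds excludes time from last dose + 29 days (57 days on the Q2M regimen). Since 28 < 29, a timely score would lie inside the SAP's own window.

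**4. Size, all inputs assumed.**
- Patients without a value = N × dropout. With the planned N = 80: 80 × 0.05 = 4; 80 × 0.10 = 8; 80 × 0.20 = 16. Haem-A-QOL would have fewer, because it covers only patients aged 17 or over in EAS 1.
- If a fraction w withdraws and their true change is worse by d points, the mean over assessed patients is too favourable by w × d: 0.05 × 5 = 0.25 points; 0.15 × 20 = 3.0 points. This applies directly to the descriptive mean, not to the mixed model.
- One worst-score imputation (assumed worst score 100, assumed true score 40, assumed n = 65) moves the mean by (100 − 40)/65 = 0.92 points, in the sensitivity analysis only.

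**5. Can the 29-day window be used to screen Month 7 scores?** Doses 28 days apart from Day 1 put the seventh monthly dose on Day 169. Table 1 sets EOT at Day 169 ± 7 and EOS at Day 197 ± 7. A compliant monthly-dosed patient's gap is 28 days nominally and ranges from 28 − 14 = 14 to 28 + 14 = 42 days. Of the 15 × 15 = 225 visit-day pairs, the gap exceeds 29 days in 13 + 12 + … + 1 = 91, about 40%. A blanket cut would remove compliant completers. It can be used only for patients who stopped fitusiran early.

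**The case against.** Four points on the other side carry weight.

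- **Fixed timing is defensible.** The comparison uses fixed assessment times. A termination score comes at variable exposure and may reflect the event that led to withdrawal. This stands, and is why the Month 7-only analysis should be kept.
- **The plan limits the gap.** Patients who stop drug are encouraged to stay, and a missing-data sensitivity analysis for Haem-A-QOL exists. This stands. A reader might infer that everyone who stops fitusiran is lost; Protocol 5.3.1 shows otherwise. A reader might also infer that the reported Haem-A-QOL result is built on worst or average scores. The SAP confines these to a sensitivity analysis, and HAL/pedHAL, TSQM-9 and EQ-5D have no such imputation.
- **The SAP would already accept such data.** Sections 2.5.4 and 2.5.5 reallocate early-withdrawal measurements and admit unscheduled efficacy values. This stands in part. Under 2.5.4 only scores from Day 183 onward fall in the Day 197 window, so an earlier termination score would not become the Month 7 value without an explicit rule.
- **Small practical effect.** HAL/pedHAL, TSQM-9 and EQ-5D are exploratory. The amendment 05 history records 79 patients enrolled, and SAP 2.4 reports only 2 on 50 mg Q2M. This stands as to yield.

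Using Month 7 scores from patients already off drug is a separate matter. It is consistent with a treatment-policy reading and is not shown to be an error, although 2.4.4.2.4 does not state the choice while the bleeding endpoints have an explicit on-treatment rule.

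**Conclusion.** The point holds for patients who withdraw from the study before Month 7: by an explicit schedule rule they have no fitusiran-period score on any of these questionnaires, and the main Haem-A-QOL model then depends implicitly on missing at random. Footnote q also sits awkwardly with footnote d and Section 5.3.2, which press for the termination visit to be completed.

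A reader might go further and infer material bias in the endpoint. The documents do not support that. They state no dropout rate and give no scores for withdrawers, so 0.25–3 points and 0.92 points only show how the result responds to assumed inputs. This is a cheap improvement to a secondary endpoint and several exploratory ones.

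**What to change.** 1. **Protocol Table 1, footnote q:** remove the ET exclusion for Haem-A-QOL/Haemo-QOL, HAL/pedHAL, TSQM-9 and EQ-5D, and record days since last fitusiran dose. HJHS may stay EOS-only. Footnote c, which waives ET assessments already done at EOT, should not waive these forms, because none is scheduled at EOT.
2. **SAP 2.4.4.2.4:** name an analysis that takes the ET score, where it exists, as the fitusiran-period value in place of worst/average imputation for those patients. Keep the Month 7-only analysis beside it. Define the average score for patients who still need imputation.
3. **Optional:** add a mixed-model sensitivity analysis that excludes Month 7 scores only for patients who permanently discontinued fitusiran early and were assessed beyond the SAP 2.1.3.1 window (29 days, or 57 for Q2M). Do not apply the window to patients who completed dosing.

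The cost is one set of self-completed forms per withdrawer at an existing visit, plus SAP wording. At this stage of enrolment the footnote change may recover few scores; the SAP clarifications in items 2 and 3 are useful either way.
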